Adolescent Attention to Emotion Study

NCT04105868

Version: 09/23/2025

Background: Rates of depression increase rapidly during adolescence, especially for girls, and, thus, research is needed to spur the development of novel interventions to prevent adolescent depression. This project sought to determine if a novel visuocortical probe of affect-biased attention (i.e., steady-state visual evoked potentials derived from EEG) could be used to modify affect-biased attention and buffer subsequent mood reactivity. This work could ultimately directly inform the development of mechanistic treatment targets to be used in personalized intervention prescriptions for high-risk youth.

Objectives: This study explored the feasibility of implementing SSVEP neurofeedback training to reduce stimulus-driven attention to negative distractors, enhance goal-directed attention, and buffer mood reactivity in response to a discrete laboratory stressor.

Outcomes:

Primary outcome: To measure change from baseline in affect-biased attention subsequently following neurofeedback.

To measure affect-biased attention, steady-state visual evoked potentials (SSVEPs) were derived from EEG and used to index the amount of stimulus-driven attention to the negative distractors relative to goal-directed attention toward task-relevant stimuli. Larger SSVEPs indicate more attention to that stimulus. Affect-biased attention was measured both before and after the real time SSVEP neurofeedback training to assess changes in affect-biased attention pre- to post-intervention. Competition indices for attention to the primary task vs negative emotional distractors at both baseline and post-intervention were calculated by dividing T-transformed SSVEP amplitudes to the task stimuli by the sum of the T-transformed amplitudes to the distractor and task stimuli. Scores above .50 reflect greater attention to the task whereas scores below .50 reflect greater attention to the distractor.

Secondary outcome 1: To measure change from baseline in sadness after a laboratory stressor, which follows neurofeedback.

Participants completed a laboratory stressor following real time SSVEP neurofeedback training to assess how well it buffered sadness reactivity. To assess sadness reactivity, girls reported state sadness before and after the stressor using Visual Analog Scales. Participants marked how they were feeling between neutral to very sad on a scale measuring 100 millimeters, with higher scores indicating greater state sadness.

Secondary outcome 2: To measure change from baseline in anxiety after a laboratory stressor, which follows neurofeedback.

Participants completed a laboratory stressor following real time SSVEP neurofeedback training to assess how well it buffered anxiety reactivity. To assess anxiety reactivity, girls reported state anxiety before and after the stressor using Visual Analog Scales. Participants marked how they are feeling between neutral to very anxious on a scale measuring 100 millimeters, with higher scores indicating greater state anxiety.

Study Design:

Design Type: Single-arm pilot study

Participants: Participants included 15 female adolescents ages 13 years 0 months through 15 years 11 months at study entry.

Exclusion Criteria:

1. Lifetime history of any DSM 5 depressive disorder
2. Lifetime history of taking antidepressants (e.g., SSRIs)
3. Lifetime history of a DSM 5 psychotic, bipolar, or autistic spectrum disorder.
4. Presence of EEG contraindications (e.g., personal lifetime history of seizures or family history of hereditary epilepsy).
5. Being pre-pubertal
6. Lifetime history of a neurological or serious medical condition.
7. Lifetime history of head injury or congenital neurological anomalies (based on parent report).
8. IQ less than 80, as assessed using the Wechsler Abbreviated Scale of Intelligence (WASI).
9. Uncorrected visual disturbance
10. Being acutely suicidal or at risk for harm to self or others.

Recruitment: 15 participants were recruited from the community.

Procedure: Girls completed one session of a task designed to give feedback on performance on an EEG-based task assessing affect-biased attention. Specifically, girls received feedback based on activity from EEG electrode sites that captured how much they were able to reduce attention to the distracting angry or sad emotional face relative to attention to task-relevant stimuli. Girls completed a laboratory stressor following the feedback task where they completed a set of anagrams, some of which were insoluble, and they were told that their performance on the task reflected intelligence. At the end of the task, they received fake negative feedback about their performance relative to peers. Girls reported state sadness and anxiety before and after the stressor using Visual Analog Scales.

Adverse Events: Adverse events were monitored continuously throughout study participation via direct report from participants and study staff observation. No adverse events were observed or reported.

Statistical Analysis Plan (SAP):

Analysis Populations:

- All participants who were enrolled (N = 15).
- Outcome-specific exclusions:
 - VAS sadness and VAS anxiety were missing for one participant at baseline; analyses were conducted on the remaining 14 participants for those measures
 - For post-stressor sadness and anxiety ratings, three participants had missing data; analyses were conducted on the remaining 12 participants
- Analyses were performed on observed data only; no imputation was used for missing data.

Primary Outcome Analysis:

- Outcome: SSVEP competition index (0-1 scale)
- Analysis: Pre- vs post-neurofeedback scores compared using a two-tailed paired samples t-test
- Null hypothesis: No mean difference in competition index from baseline to post-training
- Significance threshold: $p < .05$, two-sided
- Reported results: mean pre vs post scores, standard deviations, and p-value

Secondary Outcome Analysis 1 – VAS Sadness:

- Outcome: Self-reported sadness on a 0–100 Visual Analog Scale (VAS).
- Analysis: Pre- vs post-stressor scores compared using a two-tailed paired samples t-test
- Null hypothesis: No mean difference in sadness ratings from baseline to stressor
- Significance threshold: $p < .05$, two-sided
- Handling of missing data: 3 participants did not provide post-stressor sadness scores; analysis conducted on 12 participants.
- Reported results: mean pre vs post scores, standard deviations, and p-value

Secondary Outcome Analysis 2 – VAS Anxiety:

- Outcome: Self-reported anxiety on a 0–100 Visual Analog Scale (VAS).
- Analysis: Pre- vs post-stressor scores compared using a two-tailed paired samples t-test
- Null hypothesis: No mean difference in anxiety ratings from baseline to stressor
- Significance threshold: $p < .05$, two-sided
- Handling of missing data: 3 participants did not provide post-stressor anxiety scores; analysis conducted on 12 participants.
- Reported results: mean pre vs post scores, standard deviations, and p-value

Additional Considerations

- All tests were exploratory given the pilot nature of the study and small sample size.
- No corrections for multiple comparisons were applied.

- Analyses were performed using paired-sample t-tests only; no regression or correlation analyses were prespecified.

Power Analyses:

Because this was a pilot study, no formal *a priori* power calculations were conducted. The sample size of 15 allowed the study team to test feasibility, acceptability, and to provide preliminary analyses for future larger-scale studies. The results are considered exploratory.

Informed Consent:

All participants' legal guardians provided written informed consent and participants provided written assent. The consent document covered a broader parent study (Attention to Emotion in Adolescents), of which this pilot study was a part of. The study protocol was reviewed and approved by the University of Pittsburgh Institutional Review Board (IRB). All data were de-identified prior to analysis and confidentiality was maintained in accordance with institutional and federal guidelines.

Limitations and Caveats:

Results indicated that SSVEP competition scores decreased significantly from baseline to post-training, suggesting increased attention to emotional distractors and reduced goal task-relevant attention. There were no significant changes in reported sadness or anxiety. One possible explanation for the increase in attention to emotional distractors may be task-related fatigue.

The study had several limitations. First, the sample size was small, and analyses were underpowered to detect significant effects. Second, a single arm design limits causal inference. Third, outcomes were measured within 1 hour of completing neurofeedback and no follow-up assessments were conducted. Finally, the sample consisted only of adolescent girls, which may limit generalizability.

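### The VAS sadness and anxiety tests use complete pairs only, with 3 of 15 post-stressor ratings missing and no check on whether the missing girls reacted differently

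*Combined protocol and SAP*

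**What the plan says.** The SAP's Analysis Populations section starts from all 15 enrolled girls and then lists exclusions by outcome. At baseline, "VAS sadness and VAS anxiety were missing for one participant at baseline; analyses were conducted on the remaining 14 participants for those measures". After the stressor, "For post-stressor sadness and anxiety ratings, three participants had missing data; analyses were conducted on the remaining 12 participants". The general rule is "Analyses were performed on observed data only; no imputation was used for missing data".

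Secondary Outcome Analyses 1 and 2 use the same method: "Pre- vs post-stressor scores compared using a two-tailed paired samples t-test". For sadness, "3 participants did not provide post-stressor sadness scores; analysis conducted on 12 participants"; for anxiety, "3 participants did not provide post-stressor anxiety scores; analysis conducted on 12 participants". Additional Considerations confirms that paired t-tests are the only analyses and that all tests are exploratory.

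Limitations and Caveats reports that "There were no significant changes in reported sadness or anxiety". It lists the small sample and low power, the single arm, the short observation period and the girls-only sample. The missing ratings are not among them. The document gives no reason for the missing ratings, no comparison of girls with and without them, no stated missing-data assumption and no sensitivity analysis.

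**The concern.** A paired t-test needs both ratings from each girl, so a girl lacking either one drops out. The mean change among those who remain estimates the mean change for all 15 only if missingness is unrelated to the change, which in practice means missing completely at random. Missingness that depends only on baseline mood can already bias it.

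The rating that is missing most often comes after partly insoluble anagrams, presented as a measure of intelligence, and false negative feedback (Procedure). A girl who was more upset may have been less likely to complete the scale. If so, the mean rise in sadness or anxiety is understated. The caveat about low power concerns imprecision and does not cover a shift in the estimate. The study is also meant to supply preliminary figures for larger trials, so a biased mean change could carry forward into their planning.

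**Working it through.** **Inputs.** From the SAP: 15 enrolled, 1 without baseline VAS, 3 without post-stressor VAS, two-sided 5% level. Assumed, because no VAS mean or SD is given: SD of change 20 mm, and the range of differences shown.

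**1. The stated n.** 15 − 3 = 12 girls have a post-stressor rating. They form 12 pairs only if the girl without a baseline is one of the three. Then 2 of the 14 girls with a baseline lost the later rating. If she is a different girl, there are 15 − 3 − 1 = 11 pairs and 4/15 = 27% are excluded. The text does not say which.

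**2. Shift in the mean.** With 12 pairs, all-15 mean − observed mean = (3/15) × δ, where δ is how much more the missing girls changed. For δ = 10, 20 and 30 mm the shift is 2, 4 and 6 mm. For comparison, the 95% CI half-width with 12 pairs is 2.201 × 20/√12 = 12.7 mm.

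**3. Could the test result change?** Take n observed girls with mean m, and k missing girls with mean m + δ and the same SD s = 20. Then

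- M = m + kδ/(n + k)
- SS = (n − 1)s² + (k − 1)s² + [nk/(n + k)]δ²
- t = M / √{SS/[(n + k − 1)(n + k)]}, with n + k − 1 df.

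Observed only, m = 8, n = 12: t = 8/(20/√12) = 1.386, p = .193.

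Three girls, δ = 20: M = 12; SS = 4400 + 800 + 960 = 6160; SE = √(6160/(14 × 15)) = 5.416; t = 2.216, p = .044.

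Two girls, δ = 20: M = 10.86; SS = 4400 + 400 + 685.7 = 5485.7; SE = 5.490; t = 1.978, p = .070.

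| Observed rise | p, 12 pairs | Missing girls added | p, δ = 20 mm | p, δ = 30 mm |
|---|---|---|---|---|
| 8 mm | .193 | 3 | .044 | not needed |
| 8 mm | .193 | 2 | .070 | .058 |
| 6 mm | .321 | 3 | .086 | .062 |
| 4 mm | .503 | 3 | .162 | .113 |

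If there are instead 11 pairs, three girls with a baseline lack the later rating. At 8 mm the observed p is .214. Adding three girls at δ = 20 gives M = 12.29, SS = 4000 + 800 + 942.9 = 5742.9, SE = √(5742.9/(13 × 14)) = 5.617, t = 2.187, p = .048. So the number of pairs matters to the answer.

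In SD units, with 12 pairs and three missing girls, no common change up to 8 SD makes the result significant when the observed change is 0.2 SD (4 mm here) or less.

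**4. Bias under different mechanisms (simulation, assumed parameters).** With 20% missing, a correlation of −0.5 between baseline and change, and a log-odds slope of 1 per SD, the complete-pair bias is 0.00 SD when loss is completely random, +0.09 SD when it depends on baseline, and −0.17 SD when it depends on the change itself.

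A second simulation used 15 girls with a true rise of 12 mm and SD 20, losing three with probability weighted by exp(slope × standardised change). A slope of 0.5 gives a bias of about −2 mm and power of about 37%. Slopes of 1 to 2 give −3.7 to −5.4 mm and 26 to 31%. Random loss gives 48% power, and all 15 girls about 58%. Slopes of 1 to 2 are strong selection.

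**The case against.** The documents do not conclude that mood was unchanged. They report non-significance, call every test exploratory and admit low power. Power alone rules out a no-change reading: for a 0.5 SD change it is 35% with 12 pairs and 44% with all 15. This stands.

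A reader might infer that the VAS result is presented as evidence of buffering and that the missing girls manufacture it. The documents do not support that. No buffering claim is drawn from the VAS data, and without a control arm even complete ratings could not show buffering.

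Distress-related loss is conjecture. The Procedure says that girls completed the stressor, and no adverse events were observed or reported. If 12 is the number of pairs, one of the three missing girls had already missed the baseline rating, so upset after the stressor does not explain how her missing data began. This weakens the story for one girl but does not exclude it for the others.

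The reversal to p = .044 depends on a starting value close to the threshold and on three girls having a definable change; other plausible inputs leave the result non-significant. This stands too, and is why no claim about the actual result can be made. It does not answer the point that the assumption is unstated and untested.

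**Conclusion.** The concern holds as a gap in the analysis and reporting. Complete-pair t-tests need missingness unrelated to the change in mood; nothing in the documents supports that, and the timing of the loss gives reason for doubt. If the missing girls reacted more, the reported mean change is too small, by 2 to 6 mm for differences of 10 to 30 mm with 12 pairs.

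It would go too far to say that the non-significant findings would be overturned. That depends on unreported means and SDs: near a zero observed change the missing girls hardly matter, and around 0.4 SD they could. All p-values above rest on the assumed 20 mm SD. Severity is modest, because these are exploratory secondary outcomes of a single-arm pilot.

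**What to change.** Keep the paired t-test and, for each VAS:

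- State the number of complete pairs (12 or 11) and correct the stated n if it is 11. Give the reasons for the missing ratings where known.
- Report pre and post means on those same pairs, with the mean change and its 95% CI. Show baseline VAS for girls with and without a post-stressor rating.
- Add, labelled post hoc, a two-time-point mixed model with a small-sample df correction, using every observed rating. It covers missingness that depends on baseline but does not address loss driven by the distress itself.
- Add, also labelled post hoc, a delta (tipping-point) analysis over, say, 0 to 30 mm for the missing girls, reporting the value at which the conclusion changes, if any.
- Add one limitations sentence on the missing ratings, saying that the VAS result is inconclusive as to mood reactivity if the tipping value is plausible.

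The cost is a few extra analyses of existing data. The mixed model will gain little precision at this size, and the delta range is a judgement.

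### Does naming feasibility and acceptability as reasons for 15 participants oblige the plan to add measures or criteria for them?

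*Combined protocol and SAP*

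**What the plan says.** The Power Analyses section reports that no power calculation was made, because this was a pilot, and then gives the only rationale for the sample size: "The sample size of 15 allowed the study team to test feasibility, acceptability, and to provide preliminary analyses for future larger-scale studies". It goes on to call the results exploratory.

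The Objectives section uses the word feasibility in a particular sense: "This study explored the feasibility of implementing SSVEP neurofeedback training to reduce stimulus-driven attention to negative distractors, enhance goal-directed attention", and it adds the buffering of mood reactivity to a laboratory stressor. The outcomes are the SSVEP competition index (primary) and visual analogue ratings of sadness and anxiety (secondary). Each is compared before and after by a two-sided paired t-test at the 5% level. Additional Considerations confirms that "Analyses were performed using paired-sample t-tests only".

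Process information appears elsewhere:

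- Analysis Populations: "All participants who were enrolled (N = 15".
- Analysis Populations, baseline: "VAS sadness and VAS anxiety were missing for one participant at baseline".
- Analysis Populations, after the stressor: "For post-stressor sadness and anxiety ratings, three participants had missing data; analyses were conducted on the remaining 12 participants".
- Adverse Events: "No adverse events were observed or reported".

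On consent, the Informed Consent section notes that "The consent document covered a broader parent study", of which this pilot was a part.

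**The concern.** When a pilot has no power calculation, its stated purposes carry the whole justification for its size. Three are named here, and only the preliminary analyses have an obvious counterpart in the SAP. Acceptability is mentioned in the sample-size sentence and nowhere else. No questionnaire, rating, interview or withdrawal measure is described for it, and the mood scales record how the girls felt around a stressor, not what they thought of the training. Feasibility is the stated objective, yet nothing says what result would count as feasible. The competition index moved against the aim of the training, and Limitations and Caveats draws no feasibility conclusion from that.

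The sentence also presents the pilot as groundwork for larger studies. A team planning one would have to collect completion rates from the missing-data and safety text, would see no statement of how imprecise they are with 15 girls, and would find nothing on acceptability.

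**Working it through.** **No stated figure to reproduce.** The documents give no effect size, standard deviation, target rate or precision for 15 participants. The check therefore has two parts: whether each named purpose has a counterpart, and what a feasibility table would add.

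**Purposes set against content.**

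| Purpose named | Counterpart in the documents |
|---|---|
| Preliminary analyses | Three paired t-tests, labelled exploratory |
| Feasibility, as the Objectives frame it (can training shift attention and buffer mood?) | Competition index, sadness and anxiety; each has a null hypothesis and a threshold |
| Feasibility, as process (completion, usable data, safety) | Counts under Analysis Populations and Adverse Events, not labelled as feasibility |
| Acceptability | None described here; the parent study may hold something, but the documents do not say so |

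Only the last row is empty.

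**Intervals from the stated counts.** The exact (Clopper-Pearson) 95% interval for x of n has lower limit Beta(0.025; x, n − x + 1) and upper limit Beta(0.975; x + 1, n − x), where Beta(q; a, b) is the q-quantile. With n = 15:

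- Baseline ratings: 15 − 1 = 14, and 14/15 = 93.3% (68.1% to 99.8%).
- Post-stressor ratings: 15 − 3 = 12, and 12/15 = 80.0% (51.9% to 95.7%), a width of 95.7 − 51.9 = 43.8 points.
- Adverse events, if none means 0 of 15 girls: upper limit 1 − 0.025^(1/15) = 21.8%.
- Usable SSVEP before and after: no number is stated. Exclusions are listed only for the mood ratings, which implies 15/15, with lower limit 0.025^(1/15) = 78.2%. This is an inference, to be confirmed from study records.

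**Paired mood ratings.** The outcome is change, so both ratings are needed. If the girl without a baseline rating is among the three without a post-stressor rating, the pairs number 15 − 3 = 12, as the SAP states. If she is not, they number 15 − 3 − 1 = 11, and 11/15 = 73.3% (44.9% to 92.2%). The SAP's figure of 12 for the paired tests implies the first case.

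**Effect on the plan's results.** The t-tests use the observed values of the three outcomes. Neither a table of completion proportions nor a reworded sample-size sentence enters any of them, so every mean, standard deviation and p-value stays as it is.

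**The case for a change.** The strongest case for a change is that calling the results exploratory limits how they are read but does not supply a measure for something the document says was tested. Even if feasibility means proof of concept, no result is defined as feasible or not, so the reader cannot tell how the stated objective came out. The loss of 3 of 15 post-stressor ratings also matters for planning. Suppose, purely as an assumption, that a later study needs 100 girls with post-stressor ratings. Enrolment would be 100/0.800 = 125 at the point estimate, but from 100/0.9567 = 104.5 (105) to 100/0.5191 = 192.6 (193) across the interval. The edit would cost one word and a short table.

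Part of this stands. Acceptability is named and no measure is described, and the completion counts are not gathered under a feasibility heading. The rest carries less weight:

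- The target of 100 is not in the documents. The range treats missing ratings as a stable loss rate, although no reasons for the missingness are given, and it counts post-stressor ratings where a change score needs pairs. A planner can redo it from 12/15 with a target of their own.
- A feasibility criterion set now would be chosen with the results in view and would have no force as a criterion.
- Deleting a stated purpose, or rewording the objective, after the results are known would make the record less transparent.
- The unfavourable direction of the competition index is reported openly, with fatigue offered as one possible explanation. The small sample, the low power and the limits of a single arm are all stated.

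**Conclusion.** No change to the plan is called for. The sample-size statement is looser than the analysis behind it: acceptability has no described measure, and the process counts are reported but not summarised as feasibility. This is missing detail, and supplying it would bring no gain in the analysis. Followed exactly as written, the plan gives the same three test results and the same exploratory reading. The document does not claim that feasibility or acceptability was shown, so no conclusion rests on the gap.

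The size of the point is one word without a counterpart, plus a few proportions that follow from printed counts: 14/15 (68% to 100%), 12/15 (52% to 96%) and 0/15 (0% to 22%). A reader who needs them has the numerators and the denominator.

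This rests on three assumptions: that feasibility is read as the Objectives section frames it; that the paired mood analyses have 12 pairs, as stated; and that any acceptability data lie in the parent study or were not collected, which these documents cannot settle. If acceptability was measured, reporting it would be useful to a later study, but its absence does not weaken any analysis here.
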